# 2.2.1 Enrollment and drug dispensing irregularities

Enrollment and drug-dispensing irregularities occur whenever:

1. An enrollment is not in accordance with the protocol-defined enrollment method, such as a patient is enrolled twice.

OR

Property of the Sanofi Group - strictly confidential

2. A patient is dispensed an IMP kit not allocated by the protocol-defined allocation, such as a) a patient at any time in the study is dispensed a different treatment kit than as allocated or b) a non-enrolled patient is treated with IMP reserved for enrolled patients.

Enrollment and drug-dispensing irregularities will be monitored throughout the study and reviewed on an ongoing basis.

All enrollment and drug-dispensing irregularities will be documented in the clinical study report. The irregularities will be categorized and summarized among enrolled patients (number and percentages).

Enrollment and drug-dispensing irregularities to be prospectively identified include but are not limited to:

### Enrollment and drug allocation irregularities

Kit dispensation without IVRS transaction

Erroneous kit dispensation

Kit not available

Enrolled by error

Patient enrolled twice

#### 2.3 ANALYSIS POPULATIONS

Enrolled population: includes all screened patients with a treatment kit number allocated and recorded in the IVRS/IWRS database, regardless of whether treatment kit was used or not

For any patient enrolled more than once, only the data associated with the first enrollment will be used in any analysis population. The safety experience associated with any later enrollment will be assessed separately.

# 2.3.1 Efficacy population

The efficacy population considered for efficacy analyses will be the mITT population.

The mITT population is defined as all patients who took at least one dose or part of a dose of the open-label IMP injection and with both of the following conditions met:

- Availability of a baseline (from parent study) calculated LDL-C
- Availability of at least one calculated LDL-C during the efficacy treatment period in one of the analysis windows from Week 8 onwards.

The efficacy treatment period is defined as the time period from the first open-label IMP injection up to the day of last injection +21 days.

#### 2.3.2 Safety population

The Safety population considered for safety analyses will be the population who actually received at least one dose or part of a dose of the open-label IMP injection.

Enrolled patients for whom it is unclear whether they took the study medication will be included in the safety population.

#### 2.3.2.1 Anti-alirocumab antibody population

The anti-alirocumab antibody analysis will be performed on all treated patients (safety population) with an available ADA sample at baseline from parent study and at least one available ADA sample post first open-label IMP injection.

#### 2.3.3 Quality-of-life population

The analyses of quality of life will be performed on all enrolled and treated patients with a baseline (from parent study) and at least one matching post-baseline evaluation for any of the 5 dimensions.

#### 2.4 STATISTICAL METHODS

#### 2.4.1 Demographics and baseline characteristics

Parameters described in Section 2.1.1 including all medical history and all medical history of specific interest will be summarized in the safety population (overall as well as according to treatment received in the parent study (placebo versus alirocumab (regardless of dose)), using descriptive statistics, at baseline of the parent study and at baseline of the current study.

Continuous data will be summarized using the number of available data, mean, SD, median, minimum and maximum. First quartile (Q1) and third quartile (Q3) will be also provided for baseline lipid parameters. Categorical and ordinal data will be summarized using the number and percentage of patients.

#### 2.4.2 Prior or concomitant medications

The prior and concomitant medications will be presented for the safety population (overall and according to the treatment received in the parent study (placebo or alirocumab (regardless of dose)).

Medications will be summarized according to the WHO-D dictionary, considering the first digit of the anatomical therapeutic chemical (ATC) class (anatomic category) and the first 3 digits of the ATC class (therapeutic category). All ATC codes corresponding to a medication will be summarized, and patients will be counted once in each ATC category (anatomic or therapeutic)

linked to the medication. Therefore patients may be counted in several categories for the same medication.

The table for prior and concomitant medications will be sorted by decreasing frequency of ATC followed by therapeutic class based on the overall incidence. In case of equal frequency across anatomic or therapeutic categories, alphabetical order will be used.

Prior medications at entry into OLE will be summarized according to the WHO-DD.

In addition, concomitant lipid modifying therapies and CV medications will be summarized by pre-specified categories/therapeutic class and standardized medication name.

# 2.4.3 Extent of investigational medicinal product exposure and compliance

The extent of IMP exposure and compliance will be assessed and summarized for the safety population, overall as well as according to treatment received in the parent study (placebo versus alirocumab (regardless of dose)).

#### 2.4.3.1 Extent of investigational medicinal product exposure

The study treatment exposure (injection) will be assessed using descriptive statistics for:

Duration of OLE IMP injection exposure in weeks defined as: (date of last OLE IMP injection +14 – date of first OLE IMP injection)/7, regardless of intermittent discontinuations (see Section 2.5 for calculation in case of missing or incomplete data). Non-integer values will be rounded to one decimal place;

• The total number of OLE IMP injections by patient.

All quantitative parameters above will be summarized using number, mean, SD, median, minimum, and maximum. In addition, the duration of treatment exposure will be summarized displaying the percentage of patients according to the following categories:  $\geq 1$  day and <4,  $\geq 4$  and <8,  $\geq 8$  and <12,  $\geq 12$  and <24,  $\geq 24$  and <36,  $\geq 36$  and <52,  $\geq 52$  and <78,  $\geq 78$  and <104,  $\geq 104$  and <130,  $\geq 130$  and <156,  $\geq 156$  weeks.

In the event the manufacturer faces any performance or supply issues of the auto-injector, administrations would be done using prefilled syringes instead of autoinjectors until the end of the study. In case this back-up plan is used, the exposure to initial device and back-up device will be summarized. Analyses for key efficacy and safety endpoints will be presented by device to assess the impact of the device on study results: patients will be included in the device they received longer.

# Up-Titration/Down-Titration/maintenance of dose

The number (%) of patients with an up-titration to 150 mg/down-titration to 75 mg/maintenance of 75 mg/maintenance of 150 mg of alirocumab will be described overall and by visit, on the

Safety population. The number (%) of up-titration to 150 mg will also be summarized excluding patients coming from High FH study since these patients start the OLE study with this dose.

Reasons for up- or down-titration and LDL-C used to up/down-titrate or maintain 75/150 mg dose will be summarized, overall and by visit in order to get data about real life behavior of the investigator. LDL-C will be summarized quantitatively and with the following categories: <15,  $\ge 15$  and <25,  $\ge 25$  and <50,  $\ge 50$  and <70,  $\ge 70$  and <100,  $\ge 100$  mg/dL.

The LDL-C value and titration/maintenance of the current dose will be associated as follows:

- For each LDL-C value (calculated or measured, from central or local Lab), IVRS calls
  from x days after the sample date of this LDL-C to the sample date of the next LDL-C
  value (included) will be considered. In case several IVRS calls (for titration and for
  maintenance) are made during this time period, the selected LDL-C value will be
  associated to the titration call.
- x will depend on the minimum time needed for the availability of the LDL-C results to Investigators and will therefore be different for local lab (i.e. 1 day), calculated LDL-C from central lab (i.e. 3 days) and measured LDL-C from central lab (i.e. 7 days).
- In case no IVRS call is retrieved during the defined time period, the LDL-C value will be associated to maintenance of dose.

This analysis may also be done according to key factors (e.g. history of CV events at entry into the OLE study (Yes/No), geographical region) if the size of the subgroups permits.

In order to analyze the efficiency of the titration regimen to prevent low LDL-C compared to 150 mg administered throughout, the following analysis will be done in the subgroup of patients of the Safety population coming from LTS11717 study: number (%) of patients with 2 consecutive LDL-C <25 mg/dL during the OLE period (on titration regimen) will be compared to the number (%) of patients with 2 consecutive LDL-C <25 mg/dL during the double-blind period (on 150 mg). The same analysis will be done with 15 mg/dL threshold.

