	 Values and percent changes from baseline of the parent study in other lipids and other lipoproteins, including total cholesterol, non- high-density lipoprotein cholesterol (non-HDL-C), HDL-C, triglycerides (TGs), apolipoprotein (Apo) B, ApoA-1, ApoB/ApoA-1 ratio and Lp(a) over time in this study. 					
	Other Endpoints:					
	Anti-alirocumab antibodies assessed throughout the study.					
	 Proportion of patients who were up-titrated to 150 mg of alirocumab based on Investigator's judgment. 					
	 Proportion of patients who were down-titrated to 75 mg of alirocumab based on Investigator's judgment. 					
	 Reasons (ie, LDL-C threshold, AE) that trigger a down-titration or an up-titration of alirocumab. 					
	EQ-5D summary scores.					

ASSESSMENT SCHEDULE

Patient assessments in the OLE period

- Day 1 / Week 0 (End of treatment visit of the parent double-blind study = OLE Visit 1, except for the patients having participated in the LTS11717).
- Complete study visits: Patients will be assessed in the clinic at Weeks 4 (Visit 2), 8 (Visit 3), 12 (Visit 4), 24 (Visit 5), and then every 24 weeks until EOT Visit (Visit 17), or early termination.
- IMP dispensing visits: From Week 24, until study completion IMP dispensing visits will be scheduled every 12 weeks, in-between the clinic visits in order to allow for dispensing IMP.

Patient assessments in the FU period

 A follow up call, Visit 18, will be planned 10 weeks after the last IMP injection, ie 8 weeks after the EOT visit, for the patients who will complete the study and for the patients who will early discontinue whatever the reason.

STATISTICAL CONSIDERATIONS

Sample size determination:

As this study is an open-label extension planning to include patients from previous studies, no calculation for sample size was performed. It is expected to enroll up to 1,200 heFH patients based on the number of patients already enrolled in the parent studies.

Analysis Population:

Safety analyses will be performed on Safety population which consists of patients receiving at least one dose or partial dose of IMP in the current study.

Efficacy analyses will be performed on patients receiving at least one dose or partial dose of IMP in the current study, with a baseline (from parent study) LDL-C available and with at least one LDL-C value available in the period from first IMP injection in the current study to last IMP injection + 21 days.

Analysis of safety endpoints:

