Although the background therapies, statin at MTD or other LMT (if applicable), should be maintained stable if possible, they might be adjusted based on Investigator judgment, in particular in case of tolerability issue. The reasons of any adjustment should be documented and recorded in the e-CRF.

For adjustments based on LDL-C values, simultaneous adjustments in alirocumab dose and any LMT should be avoided.

Patients will be asked to continue to follow a stable diet (equivalent to the National Cholesterol Education Program Adult Treatment Panel III Therapeutic Lifestyle Changes (NCEP ATP III TLC) during the study.

Patients will return for regular on site visits according to the flow chart for additional laboratory testing, questionnaires, clinical examination and IMP dispensation.

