8.8.1 Management of background lipid-modifying therapy

Throughout the whole treatment period, the patients should stay, as far as possible, on the stable maximally tolerated registered daily dose of statins, with or without other LMT, that was received during the parent study.

Background LMT may be adjusted as per the Investigator's judgment, for example in case of tolerability issue. Any adjustment will be documented in the e-CRF. For adjustments based on LDL-C values, simultaneous adjustments in alirocumab dose and any LMT should be avoided.

For background LMT, including statins, sites must follow the national product label for the safety monitoring and management of patients.

Lipid profile values from samples obtained after inclusion will be blinded until week 8.

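### The SAP's summary of 'LDL-C used' to titrate or maintain the dose is not crossed with the titration reason or with LMT changes, so it pools decisions of different kinds

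*SAP*

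**What the plan says.** SAP 2.4.3.1, under the heading on up-titration, down-titration and maintenance, plans that "Reasons for up- or down-titration and LDL-C used to up/down-titrate or maintain 75/150 mg dose will be summarized, overall and by visit". It gives the purpose in the same sentence: "overall and by visit in order to get data about real life behavior of the investigator".

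The linking rule starts from the laboratory value: "For each LDL-C value (calculated or measured, from central or local Lab), IVRS calls" are searched "from x days after the sample date of this LDL-C to the sample date of the next LDL-C" value, end date included. The offset x is "different for local lab (i.e. 1 day), calculated LDL-C from central lab (i.e. 3 days) and measured LDL-C from central lab (i.e. 7 days"). If the window holds both a titration call and a maintenance call, the value goes to the titration. If it holds no call, the value goes to maintenance.

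The protocol supplies two facts that the rule does not use:

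- The Clinical Trial Summary lists as an endpoint "Reasons (ie, LDL-C threshold, AE) that trigger a down-titration or an up-titration of alirocumab", and sections 9.3.3.1 and 9.3.3.2 have these reasons recorded in the e-CRF. A titration therefore need not be driven by LDL-C.
- Background LMT may be changed during the study. Section 8.8.1 adds: "For adjustments based on LDL-C values, simultaneous adjustments in alirocumab dose and any LMT should be avoided". Section 6.1 says of LMT changes: "The reasons of any adjustment should be documented and recorded in the e-CRF".

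**The concern.** To say that an LDL-C value was used for a decision is to say something about why the decision was taken. The rule sees only which kind of call was made and when. It does not consult the recorded titration reason, and it does not look at LMT.

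This has two consequences. First, a dose change made because of an adverse event still contributes an LDL-C value to the up- or down-titration summary. Second, the protocol discourages changing alirocumab and LMT together in response to LDL-C, so an LMT change is a natural alternative response to the same value. When the investigator chooses it, the value is listed under maintenance beside values on which nothing was done.

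At stake is what the table can say about the LDL-C levels at which investigators act, which is its stated purpose.

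**Working it through.** The plan gives no figure to reproduce here. The check applies the SAP rule to the protocol schedule and then to cases that differ only in why the investigator acted.

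**Inputs.** The flow chart (Protocol 1.2) has LDL-C at Weeks 8, 24, 48 and every 24 weeks to Week 168, and IVRS/IWRS contacts at Weeks 12, 24, 36 and every 12 weeks to Week 168. Protocol 10.1.1 puts Week w on Day 7w + 1. From the SAP, x = 1, 3 or 7 days.

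**Windows.** A value sampled on day a, with the next sample on day b, covers days a + x to b, a length of b − a − x + 1 days. With x = 3:

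- Week 8 value (Day 57): Days 60 to 169, 169 − 60 + 1 = 110 days. Scheduled calls: Week 12 (Day 85, lag 28 days) and Week 24 (Day 169, lag 112 days).
- Week 24 value (Day 169): Days 172 to 337, 337 − 172 + 1 = 166 days. Scheduled calls: Week 36 (Day 253, lag 84 days) and Week 48 (Day 337, lag 168 days).
- Each later value repeats the Week 24 pattern.

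With x = 1 or 7 the later windows are 168 or 162 days long and hold the same scheduled calls. The windows are long enough for events unrelated to the LDL-C value to prompt a dose change.

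**Test cases on the Week 24 value, x = 3.**

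| What happened | Class under the SAP rule |
|---|---|
| Down-titration at Week 36, reason LDL-C | Down-titration |
| Down-titration at Week 36, reason AE | Down-titration |
| LMT changed on Day 190, resupply calls only | Maintenance |
| No change to alirocumab or LMT | Maintenance |

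Rows 1 and 2 are indistinguishable in the LDL-C summary, and so are rows 3 and 4.

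**Does the SAP separate them elsewhere?** The reasons are summarised in the same analysis, but nothing says that the LDL-C summary is split by them. The optional breakdowns give CV history and region as examples, not reason. For LMT, SAP 2.1.1 tabulates adjustments with reasons at OLE entry only. SAP 2.4.2 summarises on-study LMT by category and drug name, without a link to LDL-C or dose decisions.

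**What would set the size.** Let a be the share of down-titrations made for a reason other than LDL-C, and let m_L and m_O be the mean LDL-C at LDL-C-driven and other down-titrations. The reported mean is (1 − a)·m_L + a·m_O, so it differs from m_L by a·(m_O − m_L). None of the three terms is in the documents. Nor is the share of LDL-C values answered by an LMT change alone.

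**Gap between windows.** One window ends on day b and the next opens on day b + x. Days b + 1 to b + x − 1 belong to no value: x − 1 = 0, 2 or 6 days for x = 1, 3 or 7. Scheduled contacts fall on a sample day, 28 days after one (Week 12) or 84 days after one, so none lies in the gap. Visit windows of ±7 days do not change this for Week 12: the latest Week 8 sample (Day 64) leaves a gap to Day 70 at most, and the earliest Week 12 contact is Day 78.

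**The case against.** The case for leaving the analysis alone has several sound parts.

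- **A reader might infer that the recorded reason is ignored.** It is not. The same SAP sentence tabulates reasons, and Protocol 11.4.4 does too, so an AE-driven titration will be visible as such. Only the cross-classification with LDL-C is missing.
- **Linking by date follows the protocol.** Section 8.4 has the investigator act on the value from the previous scheduled visit, and the window is a reasonable way to find it. For an AE-driven change, the linked value is a genuine earlier LDL-C result. What fails is the label saying that it was used for the decision.
- **A reader might infer that maintenance means high LDL-C left untreated.** The SAP does not say so. It means that the alirocumab dose was kept, which is true when only LMT changes. Sections 6.1 and 8.8.1 also ask for background LMT to stay stable as far as possible and give tolerability as an example of a reason to change it. The documents therefore do not support assuming that LDL-C-driven LMT changes are common.
- **A reader might infer that the titration endpoints are compromised.** The protocol's endpoints are the proportions titrated and the reasons, and neither depends on the linking rule.

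These points limit the concern but do not remove it. The SAP sets out to describe behaviour, and as written its LDL-C summary cannot separate decisions prompted by LDL-C from those that were not.

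**Conclusion.** The point holds as a correction to one exploratory, descriptive table. The LDL-C summary for titrations pools all reasons, and the summary for maintenance pools values followed by an LMT change alone with values followed by no change.

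The size cannot be estimated from the documents, and no illustrative figure is offered because every input would be invented. If nearly all titrations are LDL-C-driven and LMT is rarely changed for LDL-C, the table will be close to right as it stands. It would therefore go too far to say that the output will show wrong LDL-C levels or will overstate inaction; it may do so to the extent that such cases occur.

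The gap between windows is real on the wording but touches no scheduled contact. It could affect only an unscheduled call, or one logged a few days after a sample. Primary safety results, lipid results and titration proportions are unaffected.

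**What to change.** Amend SAP 2.4.3.1 as follows.

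1. Summarise the LDL-C used to up- or down-titrate only for titrations whose e-CRF reason is LDL-C. Show LDL-C at titrations for an AE or another reason in separate rows, labelled as the value at the time and not as the value used.
2. Within maintenance, show separately the values followed in the window by an LMT start, stop or dose change whose recorded reason is LDL-C. SAP 2.5.3 does not impute medication dates, so count LMT changes with incomplete dates as undetermined.
3. As a minor tidy-up, end each window on the day before the next value's result can be available: next sample date + x − 1, using the x of that next value.

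No new data should be needed, since the protocol has titration reasons, LMT changes and LMT reasons recorded in the e-CRF. This assumes that the recorded LMT reason identifies LDL-C, which should be checked against the form. The cost is SAP wording, programming, a few more rows, smaller cells and some LMT changes that cannot be placed. Item 2 still assigns LMT changes by date window, so requiring LDL-C as the recorded reason is what makes the link credible.

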8.3 BLINDING PROCEDURES

From Day 1 (visit 1) until Week 8 (first unblinded LDL-C value),

- neither the treatment received during the double-blind treatment period of the parent study,
- nor the lipid parameters levels,

will be known by the Investigator and by the patient, in order to prevent any potential to jeopardize the blinding of the parent clinical study.

From Week 8 (visit 3), the lipid parameters values will be communicated to the Investigator in real time.

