8.4 METHOD OF ASSIGNING PATIENTS TO TREATMENT GROUP

This is an open-label study and every patient will receive alirocumab. Treatment kit numbers will be allocated via interactive voice/web response system (IVRS/IWRS). Patients will keep the same identification number that they were allocated in the parent study.

From Week 12 (Visit 4), the Investigator will manage, based on his/her own judgment and LDL-C value from sample obtained at the previous scheduled visit, adjustment of alirocumab doses (either up-titration from 75 mg to 150 mg every 2 weeks or down-titration from 150 mg to 75 mg every 2 weeks, or maintenance of the dose, will be possible). For adjustments based on LDL-C values, simultaneous adjustments in alirocumab dose and any LMT should be avoided.

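### The LDL-C/titration matching rule scores every blinded Day 1 LDL-C value as a decision to maintain the dose, and gives no defined outcome for the end-of-treatment value

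*SAP*

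**What the plan says.** The matching rule is in SAP 2.4.3.1, under the subheading on up-titration, down-titration and maintenance of dose.

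- **Scope:** "For each LDL-C value (calculated or measured, from central or local Lab), IVRS calls" are searched. No sample is excluded.
- **Window:** it runs "from x days after the sample date of this LDL-C to the sample date of the next LDL-C" value, that date included. The lag x is 1 day for a local result, 7 days for a measured central result, and 3 days for the usual case, "calculated LDL-C from central lab (i.e. 3 days"). The SAP justifies x by how long a result takes to reach the investigator.
- **Call types:** the sentence beginning "In case several IVRS calls (for titration and for" names titration and maintenance calls only.
- **Default:** "In case no IVRS call is retrieved during the defined time period, the LDL-C value will be associated to maintenance of dose".
- **Purpose:** the reasons for titration and the associated LDL-C "will be summarized, overall and by visit in order to get data about real life behavior of the investigator".

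The protocol fixes when a decision is possible. Section 8.3 says: "From Week 8 (visit 3), the lipid parameters values will be communicated to the Investigator in real time". Before then the investigator does not know the lipid levels. Section 8.4 says: "From Week 12 (Visit 4), the Investigator will manage, based on his/her own judgment and LDL-C value", referring to the value from the previous scheduled visit. SAP 1.1 repeats both points.

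**The concern.** The default is reasonable where an investigator has a result, could act on it, and makes no call. It is not reasonable for a value the investigator never saw, taken when the dose could not be changed. The Day 1 sample is such a value, and nothing in the algorithm removes it.

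The table is meant to show how investigators respond to LDL-C in practice. Patients from LTS11717 reach Day 1 after a washout that SAP 2.4.4.2 puts at 10 weeks, and former placebo patients have not yet had alirocumab. Their Day 1 values are likely to be high relative to on-treatment values. Pooled with later values, they would look like investigators choosing to keep the entry dose at high LDL-C.

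**Working it through.** The documents give no numerical result for this rule, so there is no figure to reproduce. The check applies the rule as written to the protocol's flow chart (section 1.2).

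**Inputs**
- Scheduled LDL-C: Weeks 0, 8, 24, 48, 72, 96, 120, 144, 168 (9 values).
- Scheduled IVRS contacts: Weeks 0, 12, every 12 weeks from 24 to 168, and 176. None at Weeks 4 or 8.
- Study day = 7 × week + 1. Visit window ±7 days.
- Window = sample day + x up to the next LDL-C sample day.

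**Windows with x = 3**

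| LDL-C value | Window | Scheduled contacts inside |
|---|---|---|
| Day 1 | Day 4 to 57 | none |
| Week 8 | Day 60 to 169 | Weeks 12, 24 |
| Week 24 | Day 172 to 337 | Weeks 36, 48 |
| Weeks 48 to 120 | same pattern | two each |
| Week 144 | Day 1012 to 1177 | Weeks 156, 168 |
| Week 168 | Day 1180, no end | Week 176 |

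With x = 1 or x = 7 the Day 1 window opens on Day 2 or Day 8 and is still empty.

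**Visit windows.** The latest Week 8 sample is Day 57 + 7 = 64. The earliest Week 12 contact is Day 85 − 7 = 78. Since 64 < 78, the Day 1 window stays empty whenever both visits are in window, and the default applies.

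**Share of scheduled values that are false Day 1 entries**
- End of treatment at Week 168: 1/9 = 11%.
- At Week 96: 1/6 = 17%.
- At Week 48: 1/4 = 25%.

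**Count.** One per patient with a Day 1 LDL-C, so at most about 1,200, the planned enrolment ceiling.

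**Effect on the maintenance share.** Take a patient with one titration and leave the end-of-treatment value out. Adding Day 1 moves the share from 6/7 = 86% to 7/8 = 88% (Week 168), from 3/4 = 75% to 4/5 = 80% (Week 96), and from 1/2 = 50% to 2/3 = 67% (Week 48).

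**Direction.** The parent-study table in protocol section 4 gives 486 + 249 + 107 + 385 = 1,227 randomised heFH patients, of whom LTS11717 supplies 385/1,227 = 31%. If entry to the extension is roughly proportional, about a third of Day 1 values follow washout, before former placebo patients from the other three studies are added. The documents do not give the size of the shift.

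**Missed Week 8 sample.** The Day 1 window then runs from Day 4 to Day 169 and contains the Week 12 and Week 24 contacts. A titration at either would be attached to the blinded Day 1 value.

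**End of treatment.** The same-day contact at the Week 168 visit (protocol 10.1.1.17) precedes sample date + x, so it is outside that value's window. With no later LDL-C sample, the window never closes. The Week 176 contact (protocol 10.1.2, Day 7 × 176 + 1 = 1233) falls inside it, but documents the end of study and is neither call type in the rule. The no-call default is not strictly triggered and no other outcome is given.

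**The case against.** **The SAP can be read as excluding Day 1.** The summary is of LDL-C used for a dose decision, and the lag is tied to when results become available. Both suggest that a withheld value was not meant to count. But the algorithm carries no such limit, and the algorithm is what will be programmed.

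**Day 1 may sit in the parent database.** For FH I, FH II and High FH, the Day 1 sample belongs to the parent study's end-of-treatment visit (protocol 10.1.1.1), so inclusion could depend on the data source. This is a real uncertainty for those three studies. For LTS11717 the lipid sample is listed among the extension's own investigations, and the SAP summarises lipids at extension baseline for everyone.

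**The damage is limited.** This stands. If rows are formed by the visit of the LDL-C sample, Day 1 has its own row and rows from Week 8 are largely clean. When Week 8 is sampled on schedule, Day 1 attracts no titration call, so LDL-C linked to titration is unchanged. Titration is an exploratory endpoint (protocol 9.3.3), and no test depends on it.

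**A stronger reading is tempting.** A reader might infer that the end-of-treatment value is also scored as maintenance, making 2 of 9 values (22%) or 2 of 4 (50%) false and the total about 2,400. The documents do not establish this. The open window contains the Week 176 contact, so the outcome depends on how a programmer treats a non-dosing call. Nor is every value without a call a non-decision: an investigator who sees a released local or unscheduled result and leaves the dose alone has maintained it, and the default records that correctly.

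**Conclusion.** Wrong as written for Day 1, undefined for end of treatment; low severity. On the planned schedule, each patient with a Day 1 LDL-C contributes one maintenance entry for a decision that was not possible: at most about 1,200 entries, and 11% to 25% of scheduled values for end of treatment between Week 168 and Week 48. The Week 48 case is illustrative, since the documents give no distribution of exits.

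The main effect is on the pooled overall summary, where the maintenance share rises and its LDL-C distribution probably moves upward. The conclusion assumes that the rule is programmed literally, that Day 1 values are in the data it reads, and that contacts occur as scheduled. It does not extend to the by-visit picture from Week 8. One exception is that values from patients stopping treatment near a scheduled week could enter that week's row.

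**What to change.** Amend the rule in SAP 2.4.3.1 as follows:

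1. Apply it only to LDL-C values released to the investigator (Week 8 onward) and obtained before the end-of-treatment visit.
2. Count only titration or re-supply IVRS calls, not contacts that document end of treatment or end of study.
3. Define the end of the window for a patient's last eligible value: the last re-supply contact, end of treatment, or the cut-off at an interim analysis.
4. Keep the maintenance default for released on-treatment values, including local and unscheduled ones.

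For a Week 168 completer this leaves 7 of 9 scheduled values (Weeks 8 to 144), each with at least one re-supply contact in its window. If Week 8 is missed, a Week 12 titration is no longer credited to the blinded Day 1 value. The cost is a few SAP sentences and a small programming change, with no new data.
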